12.4.3 Disposition of subjects

The number and percentage of subjects who were screened, enrolled, and completed the arm specific protocol, as well as the reason for discontinuation or withdrawal from the study will be presented in summary tables by treatment group and total subjects.

12.4.4 Baseline assessments

Baseline assessment summary tables will be presented by treatment group and total subjects for the ITT populations. Baseline demographics include age, gender, ethnicity, race, and transplant information including receipt of induction therapy. Baseline laboratory assessments include hematologic, renal and liver function tests. Continuous data will be presented with descriptive statistics—*N*, mean, standard deviation, median, range and interquartile range. Categorical data will be summarized by frequency distributions.

12.4.5 Duration of treatment, compliance, and participation

Duration of valganciclovir, length of study participation (while on therapy and during follow up), compliance as well as a distribution of the number of days from the date of transplantation to the date of the first dose of valganciclovir [prophylaxis arm] or date of first CMV PCR test [preemptive arm] will be summarized for the modified ITT population using descriptive statistics, including frequency distributions. For the preemptive arm the number of PCR tests, number of days between positive PCR test and the initiation of valganciclovir as well as the exposure to valganciclovir will be summarized.

Duration of valganciclovir is (date of the last dose of drug minus the date of first dose of drug plus 1 day).

Study participation as defined by the duration of the overall CMV evaluation period (while on therapy and during follow-up) will be summarized for the ITT and modified ITT populations. Evaluation period length for CMV disease assessment is (date of last study contact minus the date of randomization plus 1 day).

Receipt and duration of generic or nongeneric valganciclovir will be recorded and summarized for each study population.

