The participating sites are currently using valganciclovir prophylaxis for 100 days after liver transplantation for CMV prevention as standard of care with drug costs charged to the patient or third-party payers as part of routine clinical care. In this study, one group of subjects will continue to receive standard of care (valganciclovir prophylaxis) and the other group will receive preemptive therapy with valganciclovir only upon evidence of CMV infection. For the group randomized to preemptive therapy, the drug use is estimated to be 43% less. No additional costs for valganciclovir use for study purposes will be incurred by the participating institution, subject or another party for participants randomized to either preemptive therapy or to prophylaxis.

Use of model for end-stage liver disease (MELD) scoring system as the basis for prioritizing organ allocation by the United Network for Organ Sharing in the current era has led to a substantially higher number of patients undergoing transplantation who have renal dysfunction or are requiring dialysis than time in the previous years (53,54). In order that our study is considered representative of liver transplantation practices at present and in order for our findings to be generalized to the transplant population undergoing in current clinical settings, it is important to include liver transplant subjects that require dialysis. Data in patients on dialysis have documented no pertinent issues that could influence the pharmacokinetics and bioavailability of valganciclovir in the study subjects (55). Furthermore, all study sites are currently using valganciclovir in dialyzed patients as standard of care. Receipt of dialysis has no effect on CMV disease rate in transplant recipients. However, given higher post-transplant mortality in patients receiving dialysis (56), subjects will be stratified by receipt of dialysis and sample size calculations will take into consideration the mortality within the first year.

We propose to conduct a randomized trial comparing prophylaxis versus preemptive therapy for the prevention of CMV disease in R-/D+ liver transplant recipients. The key goals of the study are to assess the efficacy of the 2 clinically used approaches for CMV prevention and not the efficacy of the drug per se. In this regard, this is a strategy trial based on the clinical practice of medicine using a drug that is currently the standard of care in these patients.

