6.2.2.2 Preemptive therapy group

Day of randomization will be considered study Day 1 and all subsequent study days will start accordingly. Day 1 will begin immediately after randomization. In the event that a preemptive subject has already received a dose of valganciclovir as standard care prior to randomization on study Day 1: study Day 1 will still remain the day of randomization and the dose given prior to randomization will not be considered a protocol deviation. Subjects in the preemptive therapy group will undergo weekly testing of plasma using real-time CMV PCR for 100 days post randomization at the central site laboratory (see study manual for details of shipping and test result reporting). Valganciclovir 900 mg po bid (dose adjusted for renal function) will be employed upon detection of CMV viremia (at any level) and started within one week of initial positive PCR and continued until two consecutive tests performed one week apart are negative. Therapy will then be discontinued and weekly blood CMV PCR monitoring will continue until day 100 post randomization. Subjects with recurrent viremia (at any level) within 100 days post randomization will be treated with a repeat course of valganciclovir 900 mg po bid (dose adjusted for renal function) using similar criteria for discontinuation as for the initial episode of viremia. In the rare case in which viremia remains detectable at low levels or two negative PCRs cannot be achieved beyond 100 days post randomization, treatment with valganciclovir may be discontinued if the clinical team or the investigator deems that valganciclovir is no longer warranted.

All subjects assigned to the preemptive therapy group will receive acyclovir 400 mg po bid (adjusted for renal dysfunction) for at least 28 days after transplant for HSV prophylaxis as standard of care. Acyclovir will be discontinued during valganciclovir/iv ganciclovir preemptive

therapy within this period. This dose of acyclovir has no effect on CMV and is considered standard practice in the absence of routine use of valganciclovir post-transplant (53).

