7,14,21,28,35,42,49,56,63,70,77,84,91,98. All sample windows are +/-3 days. CMV PCR samples will be obtained at the transplant center if hospitalized, or will be collected during routine care follow-up clinic appointments and outpatient laboratories, skilled nursing facilities, or rehabilitation facilities. CMV PCR analysis will be completed at the University of Washington Medical Center Virology lab.

CMV PCR results will be faxed to the study site within 24 hours of receipt of blood if received Monday through Saturday. Samples received on Sundays or holidays will be resulted within 48 hours or the next business day. CMV PCR surveillance must continue at weekly intervals in preemptive subjects if continuing valganciclovir therapy after day 98 until two consecutive negative results weekly.

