7.7.2 Study day 1-107

(Drug treatment safety labs phase)
Monitoring and managing neutropenia

Neutropenia is the most commonly encountered toxicity of ganciclovir formulations (IV ganciclovir and valganciclovir). Guidance for the evaluation and management of neutropenia are provided in the study manual of operations. If necessary, administration of valganciclovir may be interrupted temporarily and subsequently re-started in response to neutropenia. If the drug has to be interrupted for more than 14 consecutive days for a given interruption episode, the site investigator may contact the study PIs to determine if there are circumstances in which it may be appropriate to re-start the drug. Otherwise, valganciclovir should be discontinued permanently and subjects should be followed as discussed in the section on handling of discontinuations.

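### The 12.4.5 formula for duration of valganciclovir counts drug-free days as treatment, mainly in the preemptive arm; the effect is confined to descriptive reporting unless the figure is reused

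*Combined protocol and SAP*

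**What the plan says.** Section 12.4.5 plans descriptive summaries in the modified ITT population, duration of valganciclovir among them, and defines that duration once, for both arms: "Duration of valganciclovir is (date of the last dose of drug minus the date of first dose of drug plus 1 day". Nothing is subtracted for days off drug, and nothing is summed over courses. For the preemptive arm alone, the same section adds PCR counts, the delay from positive test to treatment, and then "as well as the exposure to valganciclovir will be summarized". No formula for exposure follows.

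The regimens differ in how continuous the drug is. Prophylaxis is one planned 100-day course (6.2.2.1, 7.7.1). Preemptive drug is "started within one week of initial positive PCR and continued until two consecutive tests performed one week apart are negative" (6.2.2.2). The section goes on: "Therapy will then be discontinued and weekly blood CMV PCR monitoring will continue until day 100 post randomization". It then adds: "Subjects with recurrent viremia (at any level) within 100 days post randomization will be treated with a repeat course of valganciclovir". In either arm, section 7.7.2 states that "administration of valganciclovir may be interrupted temporarily and subsequently re-started in response to neutropenia".

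**The concern.** First-to-last-dose is a span. It matches days on drug only when no untreated day lies between the two dates. In the preemptive arm, untreated days between courses belong to the strategy. In the prophylaxis arm they arise only from interruptions or missed doses. The same formula therefore misstates the two arms by different amounts, and the arm meant to use drug intermittently is the one misstated more.

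At stake is the description of how much drug each strategy used. The trial compares strategies rather than drugs (2.2.2), so readers will want that description to be right. A preemptive subject treated twice for short periods could be reported with a duration close to, or longer than, the prophylaxis course.

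**Working it through.** The documents give no duration or exposure result to reproduce. The check applies the 12.4.5 formula to dosing calendars that follow the protocol's rules and compares it with days on drug.

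**Inputs**
- PCR surveillance days (7.5.3.2): "7,14,21,28,35,42,49,56,63,70,77,84,91,98. All sample windows are +/-3 days".
- Start and stop rule, and repeat courses: 6.2.2.2, as quoted above.
- Unadjusted doses (6.2.1): 900 mg once daily for prophylaxis (0.9 g/day); 900 mg twice daily for preemptive therapy (1.8 g/day).
- Interruptions of more than 14 consecutive days lead to contact with the study PIs or permanent discontinuation (7.7.2).
- Recurrence share, course lengths and gap lengths: not in the documents, so assumed and shown as ranges.

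**Formulas**
- Span (12.4.5) = last dose day − first dose day + 1.
- Days on drug = sum over courses of (stop day − start day + 1).

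**Worked subject.** PCR positive day 28, drug from day 30, negative days 42 and 49, drug stopped day 50. Recurrence day 77, drug from day 79, negative days 91 and 98, drug stopped day 99.
- Days on drug: (50 − 30 + 1) + (99 − 79 + 1) = 21 + 21 = 42.
- Span: 99 − 30 + 1 = 70.
- Difference: 28 days; 70/42 = 1.67, so 67% too long.

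**The same subject in grams, without renal adjustment**
- Actual: 42 × 1.8 = 75.6 g.
- Implied by the span: 70 × 1.8 = 126 g.
- Full prophylaxis course: 100 × 0.9 = 90 g.
- 75.6/90 = 0.84, or 16% less than prophylaxis; 126/90 = 1.40, or 40% more. For this subject the direction of the comparison reverses.

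**Other calendars**

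| Case | Drug days | Days on drug | Span | Excess |
|---|---|---|---|---|
| One preemptive course | 28-56 | 29 | 29 | 0 |
| Two courses, short gap | 28-49, 56-77 | 44 | 50 | 6 (14%) |
| Two courses, middle case | 28-49, 77-98 | 44 | 71 | 27 (61%) |
| Early course, late recurrence | 7-21, 105-119 | 30 | 113 | 83 (277%) |
| Prophylaxis, one 14-day interruption | 100-day course less 14 | 86 | 100 | 14 (16%) |

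Over an unweighted grid of 3,450 two-course calendars (stop 14 to 42 days after the positive test, start 0 to 7 days after it), the excess runs from 6 to 83 days, median 27. The median describes the grid and does not predict the trial.

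**Mean excess per treated preemptive subject** = assumed recurrence share × assumed gap, with one gap per recurring subject:

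| Recurrence share | 6-day gap | 27-day gap | 83-day gap |
|---|---|---|---|
| 20% | 1.2 | 5.4 | 16.6 |
| 50% | 3.0 | 13.5 | 41.5 |

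**The case against.** The best defence is that duration and exposure are different items in 12.4.5. Exposure is listed for exactly the arm with repeat courses, so a correct measure may be intended there. That stands in part: the plan does not say that the span is the preemptive arm's exposure. But exposure has no definition, the span is the only rule given, and prophylaxis has no matching exposure item. The only measure available for both arms is still the span.

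Compliance is also summarized, from missed doses and administration records (7.7.5), which may capture some days off drug within a course. The documents do not say whether a neutropenia interruption counts as missed doses, and compliance does not address planned gaps between courses.

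Several stronger conclusions are tempting, and the documents do not support them:
- **Neutropenia is distorted.** A reader might infer that neutropenia per treated day will look too low in the preemptive arm. No such rate is planned. Neutropenia is compared as incidence by CMH (12.6.2.1), and adverse events per person-day of follow-up (12.6.3).
- **The cost-effectiveness result is wrong.** Section 12.7.4 takes drugs received from collected data and does not cite this formula. It is affected only if this duration supplies the quantity.
- **The drug-sparing claim rests on it.** Section 2.2.2 says "For the group randomized to preemptive therapy, the drug use is estimated to be 43% less". That is a pre-trial estimate with no derivation, and section 12 plans no analysis of a saving.
- **The true saving is 58% and the formula shows 30%.** Those figures compare 42 and 70 days with 100 days and ignore twice-daily against once-daily dosing. By mass, the worked subject used 16% less.
- **The arm mean is overstated by 6 to 11 days.** That is a 28-day gap times an assumed 20-40% recurrence (5.6 to 11.2 days), and it applies to treated subjects. The modified ITT preemptive arm needs only one post-randomization PCR (12.3.2), so it includes subjects who were never treated.

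**Conclusion.** The formula is wrong as written for any subject with more than one course or an interruption, and the error falls mainly on the preemptive arm. For a two-course subject it adds 6 to 83 drug-free days under the calendars tried; in the worked case 42 days becomes 70. A prophylaxis subject with one 14-day interruption gains 14 days.

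The arm-level size cannot be fixed from the documents, because they give no recurrence rate, gap length or proportion treated. Subjects with one unbroken course are unaffected, provided the first and last dose mean study drug. Section 12.4.5 does not say so, and doses around induction (5.4.2) could otherwise lengthen the span. Some days off valganciclovir may be covered by IV ganciclovir (6.2.3), which 6.1 counts as study drug; those days are not drug-free.

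The consequence is descriptive. No primary, secondary or interim test uses the measure. It is still worth correcting before analysis, because a rule followed exactly would misreport a planned between-arm summary.

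**What to change.** In 12.4.5, for both arms:
- Define days on study drug as the sum over courses of (stop date − start date + 1), less documented interruptions. Use study drug as defined in 6.1, so that days on substituted IV ganciclovir count.
- Report number of courses, days on drug and cumulative dose by arm, with valganciclovir and IV ganciclovir doses shown separately. State how never-treated preemptive subjects enter the summary.
- Let these quantities be the definition of exposure, and name them as the drug inputs for 12.7.4.
- Keep the present formula only under the label of time from first to last dose.

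The cost is SAP wording and a little extra programming. It needs start and stop dates for each course and interruption. Section 8.1.5 lists antiviral treatment among the data collected, but the case report form is not among the documents, so the availability of these dates should be confirmed. No treatment, visit or hypothesis test changes.

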12.5 Primary outcome measures

12.5.1 Definition

The primary endpoint is the incidence of CMV disease within 12 months post-transplant. This endpoint will include all reported occurrences of CMV disease as adjudicated by the endpoint committee and/or investigator-determined CMV disease. The latter endpoint will include all reported occurrences if CMV disease by the investigator, regardless of whether they met the protocol definition of CMV disease.

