4. STUDY DESIGN

This is a /prospective, randomized, multicenter trial of prophylaxis versus preemptive therapy for the prevention of CMV disease in R-/D+ liver transplant subjects. Subjects meeting study criteria and who have provided informed consent will be randomized within 10 days post-transplant to receive, in an open label design, either prophylaxis with valganciclovir 900 mg once daily for 100 days or preemptive therapy (weekly monitoring for CMV viremia by plasma PCR weekly for 100 days post-randomization with initiation of valganciclovir 900 mg twice daily at onset of CMV viremia and continued until plasma PCR is negative on two consecutive weekly PCR tests). All dosages will be adjusted for renal dysfunction. Subjects will be followed during the intervention period (100 days post randomization) and until 12 months post-transplant for CMV disease, toxicity, and clinical outcomes (opportunistic infections, rejection, graft loss, retransplantation and mortality).

All-cause mortality, rejection episodes, graft loss and retransplantation, opportunistic infections (bacterial, fungal), need for dialysis, and post-transplant malignancies will be assessed until study closure (7 years from enrollment maximum).

Additionally, the impact of the two CMV prevention strategies on CMV-specific cellular and humoral immune responses will be evaluated at 100 days after randomization, and 6 and 12 months post-transplant.

It is anticipated that ~20-22% of all liver transplant recipients will belong to the R-/D+ group and will qualify for the study. Approximate time to enrollment will be 3.5 years. A minimum of 176 subjects will be enrolled in the study. Allowing for over-enrollment to replace dropouts, up to 205 subjects may be enrolled to achieve the target enrollment of 176 (see section 5.4.3.3). There will be a single interim analysis for the primary endpoint of CMV disease as adjudicated by an independent End Points Committee. This analysis will be conducted after~ 60 subjects have been enrolled and followed for 1 year. Study closure will occur 2 years after the enrollment of the last subject.

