8.1.4 Assessment of CMV disease

CMV disease includes **CMV syndrome** or **tissue invasive CMV disease**. The following definition will be used for the study's primary efficacy analysis:

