10 END-POINTS COMMITTEE (EPC)

10.1 Composition

An EPC will be established comprising three individuals with expertise in CMV and transplantation to adjudicate CMV disease events. The members of the EPC will be independent of the study investigators and will be selected by the DMID. The function of the committee will be to review the supporting clinical and laboratory data from all subjects identified as having developed CMV disease by the site investigators. Based on their review of the protocol definition of CMV disease and the clinical and laboratory documentation, the committee will identify those CMV disease events that should be included in the primary efficacy analysis. The EPC members will receive no financial incentives for their participation, but may be reimbursed for customary consultative or administrative support fee as determined appropriate by the DMID.

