10.2 Responsibilities and Data Flow

The role of the EPC will be to evaluate and determine if the cases reported as having CMV disease by the investigators meet the protocol definition of CMV disease. In order to do so, the EPC will review all supporting clinical and laboratory data from such cases. The committee members will be blinded to the treatment allocation of all subjects in the study, including the subjects on which they are adjudicating. Subjects will be identified only with their study number. For the purposes of review, the following specific information will be provided to the EPC for the cases:

- Narrative summary that includes description of all signs and symptoms of the illness, and the reasons that the investigator diagnosed or suspected CMV disease.
- Type of CMV disease (viral syndrome or tissue invasive disease)
- Sites of CMV organ disease.
- Laboratory assay(s) that detected CMV disease
- Biopsy findings (if applicable)
- Other relevant laboratory, imaging studies or diagnostic procedures
- Outcome of disease and treatment employed.

The coordinating center will provide the required documents to the EPC. The EPC event adjudication will occur prior to interim analysis and prior to close out. It is anticipated that there will be approximately 30 CMV disease events to be reviewed.

The EPC will provide the coordinating center and the DMID with the conclusion for all cases that it has reviewed and whether the event meets the protocol definition of CMV disease (yes or no). When a unanimous decision cannot be made on the adjudication of the case by the three committee members, a vote will be taken and the majority vote will hold.

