12.5.6 End point committee and investigator-determined CMV disease

The primary analysis will be repeated separately utilizing the adjudicated incidence of CMV disease and the investigator-determined CMV disease as the end point.

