12.6 Secondary outcome measures

12.6.1 Clinical outcomes

12.6.1.1 Incidence of late onset CMV disease [adjudicated]

The incidence of adjudicated CMV disease will be determined at the 3 and 12-month time points (late-onset CMV disease) using an analysis similar to that specified for the primary analysis of the primary endpoint and, in addition, will include separate subset analyses for CMV syndrome and CMV tissue invasive disease. The analysis will be a Cochran-Mantel-Haenszel test of the significance of the odds ratio, while controlling for the use of induction antibody therapy and renal dialysis. In addition potential prognostic factors, such as allograft rejection will be examined with a Cox proportional hazards model applied to the ITT and modified ITT populations. This analysis will be used to test the presence of a treatment effect while controlling for the various prognostic factors entered into the model. Results will be reported as the hazard ratio comparing two groups.

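### The plan does not settle whether the primary endpoint is adjudicated CMV disease or whatever the open-label investigator reports

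*Combined protocol and SAP*

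**What the plan says.** Section 12.5.1 defines the primary endpoint: "This endpoint will include all reported occurrences of CMV disease as adjudicated by the endpoint committee and/or investigator-determined CMV disease". The sentence after it adds that the investigator-determined part counts every event the investigator reports, "regardless of whether they met the protocol definition of CMV disease".

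Other sections point to a narrower endpoint:

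- Section 8.1.4 introduces the criteria for CMV syndrome and tissue-invasive disease with "The following definition will be used for the study's primary efficacy analysis".
- Section 10.1 says that, after review, "the committee will identify those CMV disease events that should be included in the primary efficacy analysis".
- Section 4 describes the interim analysis as one of the "primary endpoint of CMV disease as adjudicated by an independent End Points Committee".

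Section 12.5.4, which sets out the primary analysis, speaks only of CMV disease and names no event source. Section 12.5.6 then says: "The primary analysis will be repeated separately utilizing the adjudicated incidence of CMV disease and the investigator-determined CMV disease as the end point". For late-onset disease, a secondary endpoint, section 12.6.1.1 does name the source: "The incidence of adjudicated CMV disease will be determined at the 3 and 12-month time points".

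**The concern.** An event that the investigator calls CMV disease but that fails the section 8.1.4 criteria is in the primary analysis under 12.5.1 and out of it under 8.1.4 and 10.1. No precedence rule was found.

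Treatment is open label, and the EPC is blinded to allocation (section 10.2). Blinded adjudication is the plan's protection against knowledge of the assigned strategy affecting what counts as a case. If the investigator's list is primary, that protection does not reach the primary result. If two versions coexist without a ranking in section 12, the choice between them could be made after the results are known. The interim analysis could also use a different endpoint from the final one: section 4 ties the interim to adjudicated disease, while the stopping rules in 9.8.3 and 12.8.1 refer only to CMV disease.

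**Working it through.** **What 12.5.1 can mean**

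Under section 10.2 the EPC's task is to "evaluate and determine if the cases reported as having CMV disease by the investigators meet the protocol definition of CMV disease". It sees no other cases, so adjudicated events are a subset of investigator-determined events. Two readings follow.

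1. *Union.* Adjudicated or investigator-determined equals investigator-determined. An EPC rejection changes nothing in the primary result. Section 12.5.6 leans this way: if adjudicated disease were already primary, repeating the primary analysis with it would be redundant.
2. *Two versions.* The second sentence of 12.5.1 treats the investigator's version as an endpoint of its own, and 12.5.6 analyses the two separately. Section 12 then leaves the deciding version unnamed.

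**The plan's own figure**

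Section 12.1 states 160 subjects (80 per group) for 20% versus 5%, two-sided alpha 0.05, power 80%, by Fisher's exact test. Exact enumeration gives 79.3%. The log-rank route gives HR = ln(0.95)/ln(0.80) = 0.230, and Freedman's formula gives 20.02 events. Dividing by the mean event rate of 0.125 gives N = 160.1. The stated sample size reproduces and is not in dispute.

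**Illustration of the stakes**

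Inputs from the documents: 176 subjects allocated 1:1, so 88 per arm (sections 4 and 12.2); two-sided 0.05; CMH as primary test (12.5.4); 20% versus 5% (12.1). Assumed, because the documents give no figure: the true common incidence under the null (10% or 12.5%) and the percentage points of reported events that fail the definition.

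Method: enumerate all pairs (a, b) from two binomials with n = 88. With m = a + b and N = 176, the unstratified CMH statistic is (a − m/2)² / V, where V = 88·88·m·(N − m) / (N²(N − 1)). Reject if it exceeds 3.84. Sum the probabilities of the rejected pairs.

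*Union reading, no true difference (false-positive rate):*

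| Non-qualifying events added | True 10% | True 12.5% |
|---|---|---|
| none | 0.050 | 0.050 |
| 2 points, one arm | 0.071 | 0.066 |
| 3 points, one arm | 0.095 | 0.086 |
| 5 points, one arm | 0.168 | 0.149 |
| 8 points, one arm | 0.331 | 0.293 |
| 5 points vs 2.5 points | 0.075 | 0.071 |
| 5 points, both arms | 0.049 | 0.048 |

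*Union reading, true 20% vs 5% (power):*

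| Non-qualifying events added | Power |
|---|---|
| none | 0.883 |
| 2 / 3 / 5 / 8 points, both arms | 0.828 / 0.802 / 0.756 / 0.699 |
| 2 / 3 / 5 / 8 points, preemptive arm only | 0.732 / 0.642 / 0.459 / 0.234 |
| 5 points, prophylaxis arm only | 0.977 |

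With Fisher's exact test in place of CMH the pattern is the same at a lower level: under the null, 5 points in one arm gives 0.124 (true 10%) or 0.110 (true 12.5%), against 0.030–0.031 with none.

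*Two-version reading:* simulate 400,000 trials with no true difference and equal over-calling in both arms, and claim success if either version is significant. For 2, 3, 5 and 8 points the false-positive rate is 0.070, 0.073, 0.078 and 0.082 at a true 10%, and 0.067, 0.071, 0.075 and 0.080 at 12.5%.

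**The case against.** The best case for the plan is that 12.5.1 is an outlier. Section 10.1 gives the EPC the say over which events enter the primary efficacy analysis, and sections 4 and 8.1.4 are consistent with that, so the document as a whole favours the adjudicated endpoint. Choosing the version after seeing the data would contradict 10.1. Both versions are to be reported for the primary, late-onset and time-to-event analyses, so a discrepancy could not be hidden.

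The cross-references are also not equally strong. Section 4 mentions adjudication only for the interim analysis, 8.1.4 does not mention the EPC, and only 10.1 joins committee, definition and primary analysis.

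On size, the larger one-arm cases are extreme. Eight points on a true 10% means 8/18, or 44%, of that arm's reported cases fail the definition; five points on the preemptive arm's 5% means half do. The CMV syndrome definition is broad (viremia plus any one of several findings), which limits how many viremic cases could fail it. Section 10.2 expects about 30 cases for review, while 20% versus 5% at 88 per arm implies 88 × 0.25 = 22 true events. The excess of 8 is 8/176, about 4.5 points averaged over the arms. Eight points in both arms, about 14 events, is more than that.

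What stands: the large figures are upper illustrations, and reporting both versions makes a divergence visible. What does not stand is the inference that the conflict is therefore resolved. Section 12.5.1 is the definition in the statistical section, it expressly admits events that fail the protocol definition, and 12.5.6 ranks neither version.

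**Conclusion.** The concern holds. The primary endpoint is defined in incompatible ways, and neither 12.5.4 nor 12.5.6 settles which applies. The contradiction rests on the text alone and needs no assumption.

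Its numerical effect does depend on assumed over-call rates. Equal over-calling costs power but does not inflate the error rate under the union reading. Over-calling in one arm, or a moderate imbalance, inflates it: to about 7–8% for 5 versus 2.5 points, and to 15–17% for 5 points in one arm. Under the two-version reading, taking whichever version is significant gives 6.7–8.2% even with equal over-calling. The direction of any bias cannot be predicted from the documents. This must be fixed before any comparison by arm, because it decides which events count in the primary result of an open-label trial.

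**What to change.** In 12.5.1, name EPC-adjudicated CMV disease meeting section 8.1.4 as the single primary endpoint for both the interim and the final analysis, and delete the alternative of investigator-determined disease. In 12.5.6, keep investigator-determined disease as a labelled sensitivity analysis and drop the repeat with adjudicated disease, which would then be the primary analysis itself. Use the same endpoint name in 12.5.4, 12.8.1 and the CMV disease halting rule in 9.8.3.

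The cost is wording. Adjudication before the interim analysis and before close-out is already planned in 10.2. There may be slightly fewer primary events. The change does not recover cases that investigators never report to the EPC, nor does it remove events that meet the definition but come to light because only the preemptive arm has weekly PCR.
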